#### **Appendix-1: The standard 40-electrode array**

In addition to the 25 electrode IFCN standard including the 3 inferior electrodes F9/10, T9/10, P9/10 on each side, the following 8 intermediate electrodes are added:

[figure not shown]
FC1, FC2, FC5, FC6, CP1, CP2, CP5, CP6

and 7 electrodes for better inferior, anterior and posterior sampling:

AF11 (IO1), AF12 (IO2), AF1, AF2, PO1, PO2, Iz

These electrode locations take into account the rules of the 10-20 placement (Jaspers 1957) as accurately as possible using a relatively good estimation of the Inion (Iz).

The measurement rules will be predefined for the placement of the 40 electrodes. We will make a video on how to place the electrodes, to make sure all centers follow a standardized method.

#### **Appendix-2: Clinical and demographic data**

We intend to use the database developed by the E-epilepsy consortium (Red Cap).

The items that must be included for this study are the following:

- Patient-code: two letters for the study site code – patient number
- Age (years)
- Gender (male / female)
- Time since the start of epilepsy (years)
- MRI: normal / lesional. If lesional – specify the location using the codes in appendix-3. Add further details in free-text and image (screen-shots) in axial, coronal and sagittal planes.
- PET: normal / abnormal. If abnormal – specify the location using the codes in appendix-3. Add further details in free-text and image (screen-shots) in axial, coronal and sagittal planes.
- SPECT /SISCOM: normal / abnormal. If abnormal – specify the location using the codes in appendix-3. Add further details in free-text and image (screen-shots) in axial, coronal and sagittal planes.
- Resection: yes / no. If operated – specify the location using the codes in appendix-3. Add further details in free-text.

See the CRFs for more details on this.

### **Appendix-3: The sub-lobar regions**

See the CRF for more details.

Side: left / right

Regions:

- Frontal
  - perisylvian-superior surface / operculum
  - lateral
  - mesial
  - polar
  - orbitofrontal
- temporal
  - mesial
  - polar
  - basal
  - lateral-anterior
  - lateral-posterior
  - perisylvian-inferior surface / operculum
- central
  - lateral convexity
  - mesial
  - central sulcus – anterior surface
  - central sulcus – posterior surface
  - perisylvian-superior surface / opercular
- parietal
  - lateral-convexity
  - mesial

- perisylvian-superior surface / opercular
- occipital
  - lateral
  - mesial
  - basal
- insula

**Appendix-4:** Logging the changes in decision on clinical management of the patients:

The multidisciplinary teams take decisions in two steps:

- I. Considering all data, except ESI
- II. Adding ESI to all other data.

At each step, the decisions are classified into one of the following categories:

1. Stop (operation not recommended)
2. Implantation of intracranial electrodes
3. Operation

In addition, the changes are classified into one of the following categories:

1. No change – but concordant with decision.
2. No change – but discordant with decision.
3. Change from stop to implantation.
4. Change from implantation to stop.
5. Change in implantation plan: implantation of additional sites (besides the ones planned in step-1).
6. Change from implantation to operation.
7. Change from operation to implantation.
8. Other (specify in free text).

If changes are not related to all analyses results, it will be noted, which method(s) triggered the change (SLORETA-interictal / ictal; ECD-interictal/ictal; CLARA interictal/ictal).

At one-year follow-up, the changes are categorized as useful or not useful. A change is defined useful as follows: (a) change from stop to ICR: the ICR localized the source; (b) change in implantation strategy: the electrode(s) implanted based on the EMSI identified the source; (c) change from implantation to operation: the patient became seizure-free.

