**STUDY PROTOCOL****Prospective Multicenter Study on Localization Accuracy and Clinical Utility of Automated Electric Source Imaging in Presurgical Evaluation( PROMAESIS)**

Brief Title: Clinical Utility of Automated Electric Source Imaging in Presurgical Evaluation (PROMAESIS)

Identifiers: NCT04218812; Unique Protocol ID: PROMAESIS

Date: August 8, 2018

*Goal:* to elucidate the accuracy and the clinical utility of automated electric source imaging (ESI) in presurgical evaluation.

*Primary outcome:* accuracy measures (sensitivity, specificity, positive and negative predictive values), overall accuracy (number of [TP and TN]/total patients).

*Secondary outcomes:* clinical utility (change in patient management decisions); inter-ESI-methods agreement (at sub-lobar level).

*Patients:* consecutive patients will be prospectively recruited from the EpiCare and E-epilepsy centers.

Inclusion criteria: patients with drug resistant focal epilepsy, admitted to EMU for presurgical evaluation, who are afterwards discussed at the multidisciplinary epilepsy surgery team meetings. Exclusion criterion: patients who did not have a seizure during the monitoring.

*Sample-size:* We expect a sensitivity of 80% and specificity of 60%. We expect that 50% of the investigated patients will be operated and 66% of them will become seizure-free. Calculating with an accuracy of estimate of 10%, we need 250 patients (Hess et al., Eur J Clin Microbiol Infect Dis (2012)).

*Recordings:* Although there will be variations from center-to-center concerning the EEG electrode array, we will attempt to achieve as much standardization as possible. Centers will use either caps or cup-electrodes (mounted individually).

- a) Caps: need to be of at least 64 electrodes (10-10 system), with even spatial distribution of the electrodes, and including the inferior electrode chain. The centers will specify how they place the cap relative to fiducials and other possible reference visible on the MRI. (For example; how far is the foremost midline electrode away from Nz and the most posterior electrode from Iz; how far is the most lateral inferior electrode away from the lateral eye corner).
- b) Cup-electrodes: we need at least the standardized electrode array of 40-electrodes, described in appendix-1.

Before starting the study, we will discuss with each center the electrode array they use, and we need to validate for the study each array that will be used in the study.

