- The minimum number of spikes in a cluster must be 20 spikes

The data of each cluster should contain:

- Number of spikes in each cluster
- Waveforms of 10 examples of spikes
- Averaged waveforms and voltage maps at peak and onset.  
All waveforms (+/-500 ms around the peak) will be provided filtered with a 1 Hz forward low filter and a high filter of 70 Hz both in longitudinal bipolar and common average montages.
- Source images for the two time-points (or epochs): onset and peak (in separate images). Images should be provided in transversal, sagittal and coronal views.
- BESA will also provide source waveforms for onset and peak (only one if not substantially different) and a current vector depicting the orientation of the spike source current.
- The analyzed ictal signal for each seizure-onset epoch in common average montage with marking of the cycles/epoch that has entered the analysis.
- The source images for each seizure-onset epoch.

For the interictal EDs we will use two different definitions of the “dominant” cluster:

- Quantitative definition: the cluster with the highest number of spikes
- Qualitative definition: each center will mark a spike as dominant, in the clinical context (thus not necessarily the most prevalent cluster).

*Reference standard (“gold standard”):* For determining accuracy (sensitivity, specificity, PPV and NPV) and overall accuracy ((TP+TN)/total) gold standard will be the resected site and the outcome one year after the operation:

- TP: source is in the same sub-lobar region as the resection, seizure-free outcome
- FP: source is in the same sub-lobar region as the resection, not seizure-free outcome
- TN: source outside the sub-lobar region that was resected, not seizure-free outcome
- FN: source outside the sub-lobar region that was resected, seizure-free outcome.

To enable an adequate comparison between methods, each method should create an ellipsoid around each center location (maximum of SLORETA, equivalent dipole location(s), seeded center of cortical CLARA / CLARA) indicating the likely error in localization due to electrode/registration inaccuracies and unknown conductivities. The ellipsoid has a larger axis in radial direction (2.5 cm) as compared to the tangential axes (1.8 cm), because of the large effect of the unknown conductivities on source depth.

For determining clinical utility, the percentage of patients in whom ESI changed decision on patient management (appendix-4) will be calculated.

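### Does it matter that Appendix-4 defines a useful change for only three of its six change codes?

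*Protocol*

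**What the plan says.** Under Appendix-4 the team decides twice, first without ESI and then with it, and each decision is placed in one of three categories ("At each step, the decisions are classified into one of the following categories"). The difference between the two steps then receives one of eight codes. Codes 1 and 2 mean no change; codes 3 to 8 are changes, and code 8 is a free-text remainder.

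The appendix continues: "At one-year follow-up, the changes are categorized as useful or not useful". The definition opens with "A change is defined useful as follows: (a) change from stop to ICR: the ICR localized the source", adds a criterion (b) for an altered implantation strategy, and closes with "c) change from implantation to operation: the patient became seizure-free". No criterion follows for "Change from implantation to stop" (code 4), for "Change from operation to implantation" (code 7) or for code 8.

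The outcome itself is set elsewhere. The list of secondary outcomes at the start of the protocol has "clinical utility (change in patient management decisions", and the end of the reference-standard section fixes the measure: "the percentage of patients in whom ESI changed decision on patient management (appendix-4) will be calculated".

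**The concern.** The sentence requiring the rating speaks of the changes without limiting them to certain codes, yet the definition covers only some of them. Two readings are open. If the three criteria are exhaustive, a change coded 4, 7 or 8 is not useful whatever happened to the patient. If they are not, such a change cannot be rated although a rating is called for. The text does not choose.

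Any summary of the ratings would then depend on the mix of change types and on the reading adopted, as well as on whether ESI helped. The omission also has a direction. The covered codes all move towards more invasive work-up or surgery, while the two named codes without a criterion step back from it. A literal reading could therefore count against ESI whenever it led a team to hold back.

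**Working it through.** **Step 1: match codes to criteria.** All inputs come from Appendix-4.

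| Code | Change | Criterion |
|---|---|---|
| 3 | stop to implantation | (a) |
| 4 | implantation to stop | none |
| 5 | additional implantation sites | (b) |
| 6 | implantation to operation | (c) |
| 7 | operation to implantation | none |
| 8 | other, free text | none |

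Three of six change codes have a criterion and three do not. For code 5 the wording of the code and of criterion (b) differs slightly, but the match is clear. Criterion (a) cannot be stretched to code 7, because it is limited to changes that start from stop. No other part of the protocol supplies a missing criterion. A preset rule is hardly to be expected for a free-text category, so the plain gaps are codes 4 and 7.

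**Step 2: see which stated results use the rating.**

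- Primary outcome (sensitivity, specificity, predictive values, overall accuracy): built from source location, resected region and one-year seizure outcome. The rating is not used.
- Clinical utility: patients with a changed decision divided by patients assessed. Codes 3 to 8 all count in the numerator. The rating is not used.
- Agreement between ESI methods: the rating is not used.

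The effect on each stated outcome is therefore zero.

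**Step 3: size the effect on a usefulness share, if someone reported one.** The protocol plans no such share, so this is only a bound on what could be at stake. Let u be the share of changes in codes 4, 7 and 8, and r the useful rate among changes that have a criterion.

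- Rating only the codes with a criterion gives r.
- Treating the three criteria as exhaustive gives (1 − u) × r.
- The difference is r − (1 − u) × r = u × r.

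The protocol gives neither u nor r. With r assumed to be 70%:

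- u = 10%: 0.9 × 0.70 = 63%, a difference of 7 points.
- u = 20%: 0.8 × 0.70 = 56%, a difference of 14 points.
- u = 40%: 0.6 × 0.70 = 42%, a difference of 28 points.

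These figures show only that a larger unrated share matters more. They are no estimate for this study.

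**Step 4: check whether the gap can be closed from recorded data.** The step I decision, the step II decision and the change code are all logged. Any summary can be split by code, and codes 4, 7 and 8 can be set apart at analysis. No item that would be needed later is lost.

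**The case for a change.** The strongest case for acting is that the protocol took this definition on itself, so it cannot simply be passed to an analysis plan. It wrote a rule that sounds complete and does not cover its own code list. The one-year rating is also the only place where the study asks whether a change helped, as opposed to whether it occurred. The centres supply the data on management changes, so like cases might be handled differently, and one or two sentences would settle the matter.

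Much of this stands: the mismatch is there, its direction is worth knowing, and clarification would be cheap. Two parts are weaker. Uneven rating between centres is inferred, because Appendix-4 does not say who assigns the rating. And which changes enter a usefulness summary, and how those without a criterion are shown, is the kind of detail commonly left to a statistical analysis plan, which is not at hand here.

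The obvious repair has a flaw of its own. Declaring codes 4, 7 and 8 not assessable as a block would go further than the text supports. Code 7 leads to an intracranial recording, the same kind of evidence that criterion (a) relies on. What would count as useful there is for the investigators to say.

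**Conclusion.** The observation is correct but calls for no change. It is a gap in a descriptive rating that supports no stated outcome. The primary accuracy measures and the percentage of patients with a changed decision are the same under either reading.

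The sensible handling is available as the protocol stands: apply the three criteria where they fit, show the remaining codes separately with their counts, and give the denominator. A careful analyst would do this anyway, ideally settling it before one-year outcomes are read.

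The conclusion rests on two conditions: that clinical utility is reported as the protocol defines it, and that the rating stays descriptive. If a usefulness percentage were made a headline result, the treatment of codes 4 and 7 would have to be fixed first, since the two readings would then differ by u × r, an amount the protocol does not allow anyone to estimate.
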